Feasibility: The primary mentor's lab has been successfully recruiting, on average, one trauma-exposed participant/week. A pilot study will be conducted during the current KL2 to address potential barriers for recruitment and retention of participants. In the R21 funded study, approximately a half of participants met inclusion criteria and completed at least first two WNE sessions (Fig. 2). Therefore, we expect to enroll 140 participants during the 40-month K01 recruitment period (3.5/month), and ~70 of them would complete at least first two WNE sessions. Based on the previous retention rate, we estimate that 54 participants (27 in each group) would complete the entire protocol. Reasons for dropouts from the R21 study included time conflicts and a family emergency. No participants reported distress related to WNE as a reason for withdrawal.

Assessment: Screening and self-report measures. The initial phone screening will include questions about excluded conditions, trauma exposure, and PTSD symptoms (using the Primary Care PTSD screen,⁶¹ a 4-item screener). The questionnaire package includes a demographic questionnaire, the Life Event Checklist (LEC)⁵⁵ to determine the most stressful event (the index trauma), and a sleep questionnaire developed in the mentor's lab to assess habitual sleep schedule and signs of possible narcolepsy.

Medical/physical tests. Vital signs, height, and weight will be measured, and a physical examination will be performed by a physician or a nurse practitioner. Urine toxicology screening (all participants) and a urine pregnancy test (all female participants) will be conducted by a nurse at the CRU.

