Study Medication: Suvorexant, a dual orexin receptor antagonist, is the first and only FDA-approved agent in this class for treatment of insomnia. Over 2,000 patients with insomnia have been exposed to suvorexant in one 4-week Phase IIB, two 3-month Phase III, and one 1-year Phase III trials.^{48,49,68} Suvorexant (both 10 mg and 20 mg) reduced PSG-measured WASO and increased total sleep time, sleep efficiency, and REM sleep on the first night and at 4-week follow-up. In the largest trial, 20 mg (non-elderly)/15 mg (elderly) suvorexant increased SWS on the first night in patients with insomnia, and the effect was greater with a higher dose, 40/30 mg.⁵⁰ No gender differences were found in its effects on self-reported or PSG outcomes or its safety.^{48,60,69} The most common adverse effect was somnolence which occurred in 7% of insomnia patients receiving 20/15 mg, daily for 3 months compared with 3% receiving placebo. Other adverse events included nasopharyngitis (5%) and headache (7%), although these rates were comparable to the rates for those receiving placebo. Only 3% of the 3-month trial participants receiving suvorexant discontinued treatment due to adverse effects, which was comparable to the rate for those receiving placebo. The recommended dose is 10 mg, once daily, and the maximum recommended dose is 20 mg. The prescription information provided by Merck instructs to take the medication within 30 minutes of going to bed and stay in bed for at least 7 hours.⁶⁰ Given that suvorexant's effects on SWS were stronger with the higher doses, in this study, the dose will be increased from 10 mg at the 1st administration to 20 mg at the 2nd administration if the participant tolerated the lower dose well. The 2nd dose will remain at 10 mg if the participant had mild to moderate sedation in the morning after the 1st administration. If the participant had significant adverse events (that is rare), he/she will not have the 2nd administration. The CRU nurse and the study staff will monitor participants' alertness level in the following morning, and those who remain at a low alertness level will be prohibited from driving themselves.

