Statistical Analysis Plan

Official Title: Can Blocking the Orexin System Enhance Sleep's Benefits to Therapeutic Exposure for PTSD?

NCT number: NCT02849548

Date of the Document: July 7,2016

Data Analysis Plan: Initially, data will be pre-screened for errors, outliers, normality of distributions, and any necessary modifications such as transformation will then be conducted. The suvorexant and placebo groups will be compared on demographics and baseline measures using *t*-tests or chi-squared tests to examine group comparability. Fig. 1 describes each hypothesis. **Hypothesis 1a:** The primary comparison will be between the 2 groups (suvorexant vs. placebo) and sleep parameters measured at 3 time points (baseline, post-Session 1, and post-Session 3). A repeated-measures ANOVA will be performed to examine whether there is a Group x Time interaction effect on each sleep parameter of interest (i.e., N3, WASO, and REM sleep). If a significant interaction effect is found, group comparisons will be performed at each time point. **Hypothesis 1b:** A repeated-measures ANOVA will be performed to examine whether there is a Group x Time interaction effect on CAPS scores. In addition, 2(Group) x 2(Time) ANOVAs will be performed to examine if there is an interaction effect on intersession habituation between Session 1 & 2 and between Session 3 & 4, using a baseline-corrected highest average pulse rate as a dependent variable. **Hypothesis 1c:** To examine indirect effects of suvorexant on PTSD through the mediator, post-WNE sleep change, a path analysis using bootstrapping procedures will be performed for each sleep parameter of interest using SPSS macros developed by Preacher & Hayes.⁷⁰ Baseline CAPS scores will be included as a covariate. The same method will be used to examine indirect effects of suvorexant on intersession habituation.

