Power considerations. G*Power⁷¹ was used to perform power analysis. $\alpha = .05$ was applied in all analyses. We estimate that 54 participants (27 in each group) will complete protocol (see the Feasibility section). **Hypothesis 1a:** The primary outcomes for power evaluation are WASO and REM sleep. The prior studies suggest small effects of suvorexant on N3; therefore, it was not considered for power evaluation. Herring et al's clinical trials^{48,50} showed that effect sizes of one night of 20/15mg suvorexant on WASO and REM sleep (minutes and %) were $f = -0.37$, 0.32, and 0.22, respectively. A total of 16, 22, and 50 participants are needed to detect a Group x Time effect on WASO and REM sleep in minutes and percentage, respectively, with 80% power. Since no studies have examined effects of suvorexant on PTSD, power analysis for **Hypothesis 1b** is based on effect sizes found in Taylor et al's⁴⁴ clinical trial of prazosin in civilian outpatients with PTSD. 12 participants are needed to detect the effect size found in this trial ($f = 0.40$). **Hypothesis 1c:** Sizes of the indirect effects of suvorexant on PTSD and intersession habituation through post-WNE sleep change are unknown. We selected the bootstrapping procedure as it is more powerful than Sobel test.⁷²

The proposed study also includes comparisons of several other variables. The relative sample size required for multiple comparisons of variables (between 10-20) allowing for Bonferroni-adjusted test to achieve 80% power relative to the sample size required for a nominal is only 3.⁷³ The proposed sample size of 54 will, therefore, have adequate power to detect medium to large effects in our planned analyses. Statistical significance of effects and their clinical importance will be carefully considered in data interpretation to inform the development of subsequent grant applications.

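### Are the sleep sample sizes of 16, 22 and 50 wrong because no single correlation reproduces them and the kind of effect size is not stated?

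*SAP*

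**What the plan says.** Hypothesis 1a (SAP, Data Analysis Plan) is tested by a repeated-measures ANOVA for a Group x Time interaction, with two groups and "sleep parameters measured at 3 time points (baseline, post-Session 1, and post-Session 3". The section on power considerations names G*Power, alpha 0.05 and 80% power. It says that in earlier insomnia trials the "effect sizes of one night of 20/15mg suvorexant on WASO and REM sleep (minutes and %) were" -0.37, 0.32 and 0.22. The next sentence converts these into sample sizes: "A total of 16, 22, and 50 participants are needed to detect a Group x Time effect on WASO and REM sleep", the last two being for REM sleep in minutes and in percentage. The section concludes: "The proposed sample size of 54 will, therefore, have adequate power to detect medium to large effects in our planned analyses".

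The 54 is not derived from these totals. It comes from the protocol's Feasibility section, where, from the retention seen in the previous study, "we estimate that 54 participants (27 in each group) would complete the entire protocol".

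**The concern.** Two things look wrong. First, a sample size for a within-between interaction depends on the correlation between repeated measures, and the SAP states none. Solving backwards, the correlation that yields 50 for REM percentage is lower than the one that yields 16 for WASO, and the two ranges do not meet. That suggests a slip in at least one total.

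Second, the f values are described as effects of one night of drug but are used for an interaction over three time points. If each f is really half of a standardised group difference on a single night, the interaction f is less than half as large and the required totals are several times larger. WASO and REM sleep are the outcomes chosen for power evaluation, and sleep change is the mediator in Hypothesis 1c. If power for REM sleep were well below 80%, the closing statement on adequate power would be too favourable and a null REM result would say less than it seems to.

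**Working it through.** **Inputs.** From the SAP: alpha 0.05, power 0.80, 2 groups, m = 3 time points, f = 0.37, 0.32 and 0.22 (the minus sign on 0.37 is taken as direction only), N = 54. Not in the documents, so assumed: correlation ρ, varied; sphericity (ε = 1) unless noted; compound symmetry.

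**Formula.** For the within-between interaction, λ = f²·N·m·ε/(1−ρ), with df1 = (m−1)ε and df2 = (N−2)(m−1)ε. Power is the upper tail of the noncentral F. N rises in steps of 2.

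**Step 1: reproduce 16, 22 and 50, entering f directly.**

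| ρ | WASO | REM min | REM % |
|---|---|---|---|
| 0.30 | 20 | 24 | 48 |
| 0.32 | 18 | 24 | 48 |
| 0.40 | 16 | 22 | 42 |
| 0.50 | 14 | 18 | 36 |

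Exact matches need ρ of 0.39–0.47 for 16, 0.35–0.41 for 22 and 0.27–0.30 for 50. The first two ranges overlap; the third meets neither. Allowing for rounding of f does not close the gap: 50 then needs ρ of at most about 0.33, and 16 at least about 0.37.

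Taking each outcome separately:
- WASO, ρ = 0.43: λ = 0.37²·16·3/0.57 = 11.53, power 83%; N = 14 gives 76%.
- REM minutes, ρ = 0.38: λ = 0.32²·22·3/0.62 = 10.90, power 82%; N = 20 gives 78%.
- REM %, ρ = 0.28: λ = 0.22²·50·3/0.72 = 10.08, power 81%; N = 48 gives 79%.

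So all three totals are correct minimum sample sizes at ordinary correlations that differ by outcome. With one common ρ of 0.32, the stated totals give 75%, 78% and 83% power.

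**Step 2: power at N = 54 if f is the interaction effect.**

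| ρ | WASO | REM min | REM % |
|---|---|---|---|
| 0 | 99% | 96% | 70% |
| 0.3 | >99% | 99% | 85% |
| 0.5 | >99% | >99% | 95% |

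REM % reaches 80% at ρ of about 0.21 (λ = 0.22²·54·3/0.79 = 9.93). With ε = 0.75 it has 77% at ρ = 0.3 and 89% at ρ = 0.5.

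**Step 3: power at N = 54 if f is half a one-night standardised difference.** Assume d = 2f, no difference at baseline and the same difference on both later nights. The interaction f is then f·√2/3, which gives 0.174, 0.151 and 0.104.

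| ρ | N needed | Power at 54 |
|---|---|---|
| 0.3 | 76 / 102 / 212 | 65 / 51 / 27% |
| 0.5 | 56 / 74 / 152 | 80 / 67 / 36% |
| 0.7 | 34 / 44 / 92 | 96 / 88 / 56% |
| 0.85 | 18 / 24 / 48 | >99 / >99 / 86% |

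If f is instead an effect on change from baseline, in SDs of change, the ρ = 0.5 row applies whatever the correlation.

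**Step 4: the closing statement in the SAP's own metric.** For a conventional medium f of 0.25 at N = 54, λ = 0.25²·54·3/(1−ρ) = 10.1, 14.5 and 20.3 at ρ = 0, 0.3 and 0.5. Power is 81%, 93% and 98%.

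**The case for a change.** The strongest case for a change is that the SAP itself labels the f values as one-night effects and shows no conversion. The totals cannot settle the matter: the interaction reading at ρ of about 0.32 and the halved-difference reading at ρ of about 0.85 both give 18, 24 and 48. Under the second reading REM minutes has d = 2 × 0.32 = 0.64, inside the medium-to-large range, and 54 completers fall short of 80% at ρ = 0.5. Rewriting two sentences would cost little.

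The ambiguity stands, and so does the arithmetic. What does not follow is that the plan is wrong. The low figures need f = d/2 and an assumed pattern over time, and only the cited trials could confirm the former. Where the halved reading comes close to the SAP's own totals (ρ of about 0.85), it gives 86% or more at N = 54 for all three outcomes. At correlations of 0.3 to 0.7 it needs totals far from 16, 22 and 50, so the low-power figures apply only if the wrong kind of f was entered, which is possible but not shown. A null REM result would in any case be judged on its estimate and confidence interval.

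Two related points add no error. For CAPS, "12 participants are needed to detect the effect size found in this trial" reproduces at f = 0.40, three measurements and ρ = 0.5. The effect sizes are for 20/15 mg, while dosing starts at 10 mg and "The 2nd dose will remain at 10 mg if the participant had mild to moderate sedation in the morning after the 1st administration"; but the protocol's Study Medication section also reports that "Suvorexant (both 10 mg and 20 mg) reduced PSG-measured WASO and increased total sleep time, sleep efficiency, and REM sleep on the first night", so the documents do not contradict each other on whether an effect is expected at the lower dose.

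**Conclusion.** No change to the plan follows. The SAP never says that one correlation was used for three different sleep outcomes, and each total is reproduced exactly at a plausible value of its own. A single value of about 0.32 comes within 2 of all three. No stated figure is shown to be wrong.

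On the plain use of the SAP's numbers, with f as the Group x Time effect and sphericity, 54 completers give at least 80% power for WASO and REM minutes at any non-negative correlation, and for REM percentage from a correlation of about 0.21. The conclusion about medium to large effects holds for f = 0.25 even at zero correlation (81%). The much lower figures, 65%, 51% and 27% at a correlation of 0.3, depend on a reading of the cited effect sizes that cannot be checked from the documents.

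What remains is missing detail: the correlation, the sphericity assumption, the number of measurements entered and the kind of f. Recording these would be good practice, but it would alter neither enrolment, which rests on expected retention, nor the analysis.

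### The SAP's adequate-power sentence does not except the Hypothesis 1c mediation analyses, for which no power was calculated and 54 participants fall short of 80% in the medium-path cases examined

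*SAP*

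**What the plan says.** The Data Analysis Plan section of the SAP sets out Hypothesis 1c: "a path analysis using bootstrapping procedures will be performed for each sleep parameter of interest", with baseline CAPS as a covariate, and the same method for intersession habituation. The sleep parameters of interest, named under Hypothesis 1a, are N3, WASO and REM sleep.

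The Power considerations section works from completers: "We estimate that 54 participants (27 in each group) will complete protocol". For Hypothesis 1a it takes effect sizes f of 0.37 (WASO, in absolute value), 0.32 (REM minutes) and 0.22 (REM %), and states: "A total of 16, 22, and 50 participants are needed to detect a Group x Time effect", at 80% power. For Hypothesis 1b it takes f = 0.40 and states 12 participants. For Hypothesis 1c it states: "Sizes of the indirect effects of suvorexant on PTSD and intersession habituation through post-WNE sleep change are unknown". The only further argument there is that the bootstrap has more power than the Sobel test.

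After a sentence on multiple comparisons, the section concludes: "The proposed sample size of 54 will, therefore, have adequate power to detect medium to large effects in our planned analyses". It makes no exception for Hypothesis 1c.

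**The concern.** More power than the Sobel test is a relative statement and says nothing about whether power is adequate. An indirect effect is the product of two paths, drug to sleep and sleep to outcome, and both must be detectable before the product is. The sample sizes stated for the Group x Time ANOVAs therefore do not carry over to the path analyses.

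Hypothesis 1c asks the mechanistic question of the trial, whether the drug helps through sleep. The SAP says that results will inform later grant applications. If the adequacy claim stands, a bootstrap interval that includes zero could be taken as evidence against mediation, although the design may often miss mediation of medium size.

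**Working it through.** **1. The plan's own figures (ANOVAs).** For a within-between interaction with two groups and m time points, λ = f²·N·m/(1−ρ), with m−1 and (N−2)(m−1) degrees of freedom. The SAP gives neither m nor the correlation ρ used in its power calculation. Total N for 80% power at α = 0.05:

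| Setting | f = 0.37 | f = 0.32 | f = 0.22 | f = 0.40 |
|---|---|---|---|---|
| SAP | 16 | 22 | 50 | 12 |
| m = 2, ρ = 0.5 | 18 | 22 | 44 | 16 |
| m = 3, ρ = 0.5 | 14 | 18 | 36 | 12 |
| m = 3, ρ = 0.3 | 20 | 24 | 48 | 16 |

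No single setting tried returns all four. Each is approximately met under some setting, so they are not shown to be wrong. For a medium f = 0.25 at N = 54 and ρ = 0.5, λ = 0.0625 × 54 × 2/0.5 = 13.5 (m = 2), giving 95% power; m = 3 gives 98%. For the ANOVAs the adequacy claim holds under this assumption.

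**2. Inputs for Hypothesis 1c.** From the SAP: 27 per arm, α = 0.05, baseline CAPS as covariate, 80% as the target used for the sleep outcomes. Assumed, because the documents do not say: a two-sided 95% interval, percentile or bias-corrected; path a as a standardised difference d in sleep change; path b as the partial correlation r of sleep change with the outcome given arm and baseline CAPS; no direct effect.

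**3. Closed-form check of one conventional medium case (d = 0.5, r = 0.30).**
- Path a: noncentrality d·√(27/2) = 0.5 × 3.674 = 1.84; power 44%.
- Path b: noncentrality r/√(1−r²)·√54 = 0.3145 × 7.348 = 2.31; power 62%.
- Both significant: 0.438 × 0.620 = 0.27.

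With r = 0.30, the 62% for path b caps this product however large the drug effect on sleep is.

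**4. A more generous medium for path a.** Equating λ with d²N/4 gives d = 2f·√(m/(1−ρ)). With m = 2 and ρ = 0.5 this is 4f, so f = 0.25 corresponds to a change-score d of 1.0.

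**5. Simulation.** N = 54, a covariate in both regressions, 800 to 1,000 bootstrap resamples, at least 1,000 simulated trials per case. Where a case was run more than once, the spread is shown.

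| Path a | Path b | Percentile | Bias-corrected |
|---|---|---|---|
| d = 0.5 | r = 0.30 | 24–27% | 35–38% |
| d = 0.5 | slope 0.39 (r ≈ 0.36) | 32% | 43% |
| about 0.30 as a correlation | r = 0.30 | 36% | 47% |
| 0.39 standardised | slope 0.39 | 60% | 72% |
| d = 1.0 | r = 0.30 | 58% | 67% |
| d = 1.0 | slope 0.39 | 72–74% | 79–80% |
| d = 1.5 | r = 0.30 | 61% | 65–66% |
| d = 1.5 | r = 0.40 | 85–87% | 87–89% |
| d = 0.8 | r = 0.50 | 79–81% | 84–85% |

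The first six rows are readings of two medium paths. The rows at d = 1.5 use, rounded, the value that the SAP's WASO effect gives on the conversion in step 4 (4 × 0.37 = 1.48).

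**The case against.** The closing sentence sits in a paragraph about comparisons of other variables, and its inference follows from a multiplicity argument. It could be read as covering comparisons only. The SAP also discloses, a few lines earlier, that the Hypothesis 1c effect sizes are unknown. Both observations are fair. But the sentence refers to the planned analyses without exception, Hypothesis 1c is one of them, and admitting that the effect is unknown does not support a claim of adequate power for it.

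Several stronger readings are tempting, and the documents do not support them:

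- *Power for medium paths is about a quarter to a third.* That is one case. The documents do not define medium, and other readings run up to about 80%.
- *Power can be computed for each sleep parameter by taking d as twice the SAP's f.* This conflicts with the SAP's own sample sizes. If the interaction is treated as a two-group test of change, d = 0.74, 0.64 and 0.44 give only 28%, 30% and 33% power at N = 16, 22 and 50, where the SAP claims 80%.
- *Only two large paths reach 80%.* A very large path a (d = 1.5) with r = 0.40 gives 85% to 89%.
- *N3 contradicts the claim.* The SAP expects a small effect of suvorexant on N3, and the sentence concerns medium to large effects. N3 is a planned mediator that lies outside the claim, so it does not refute it.
- *The SAP contains an arithmetic error here.* It gives no Hypothesis 1c figure that could be wrong. The fault is a conclusion that reaches further than the calculations behind it.

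No text says that a null mediation result will be read as absence of mediation. That harm is a risk the wording leaves open, and is not something the plan proposes.

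**Conclusion.** The point holds in limited form. The adequacy sentence includes Hypothesis 1c on its plain reading, no calculation supports it there, and it sits badly with the SAP's own statement that the effect sizes are unknown.

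At 27 per arm, power is about 25% to 38% for d = 0.5 with r = 0.30, and about 58% to about 80% with a change-score d up to 1.0 and path b between 0.30 and 0.39. The top of that range only just touches the target, and only with the bias-corrected interval. If the sleep-CAPS link is r = 0.30, power stays below 70% even at d = 1.5. The large end of the claim is roughly met, at about 80% to 85% for d = 0.8 with r = 0.50.

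These figures rest on the path sizes, interval types and simple model stated in the working, at an unadjusted 0.05. Any multiplicity adjustment across the mediation models would lower them.

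**What to change.** In the Power considerations section of the SAP:

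- Limit the adequate-power sentence to the Hypothesis 1a and 1b ANOVAs for which power was calculated.
- State that Hypothesis 1c is exploratory and is not powered at 80% for medium paths. Give the range with its assumptions: about 25% to 38% for d = 0.5 and r = 0.30; about 58% to about 80% for a change-score d up to 1.0 and path b 0.30 to 0.39; about 80% to 85% for d = 0.8 and r = 0.50.
- Note that N3 is kept as a mediator with an expected small effect and falls outside the power claim.
- Under Hypothesis 1c, commit to reporting each indirect effect with its bootstrap interval, and state that an interval including zero will not be interpreted as absence of mediation.

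This is a change of SAP wording only. Sample size, procedures and treatment are untouched. The cost is that a stated power claim becomes less favourable.
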